#### Study Phase - Run-in Phase:

The purpose of the run-in phase (2 to 4 weeks) is to train the subject's parent(s)/legal guardian(s) on the MiniMed 780G system in Manual Mode with Suspend before low activated and to collect 2 weeks of baseline data.

At the end of Run-in Phase, subjects will be randomized into 2 sequences (A and B).

Successful completion of run-in phase requires sensor usage  $\geq$ 70% over the previous 2 weeks during the run-in phase. If this is not achieved (e.g. sensor felt off) the run-in phase can be extended for another 7 to 14 days to achieve sensor usage  $\geq$ 70%.

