# 7.4 Handling of Missing, Unused, and Spurious Data and Dropouts

The Primary endpoints analyses are based on ITT using a random effect model that uses available data and accounts for missing at random. In addition, sensitivity analyses will be performed on PP set.

For per protocol analysis, if A1c is collected out of window (± 14 days from target visit date) A1c will be considered missing for that particular period/visit.

For the Run-in period, glycemic variability metrics from device data will be derived if a minimum number of 2880 of SG values (288 SG values/day × 10 days out of 14 days) is available, otherwise that data will be considered as missing.

In the case of dates collected at baseline with missing day and/or month the next procedure will be applied. A missing day and month will be imputed using the month 'July 1' and a missing day will be imputed with the day '15'. This applies only to dates related to medical history and baseline information with missing month and/or day.

For tables and listings of safety data a conservative/worst case scenario approach will be taken in case of partially missing dates. For the date of discharge with missing day, the day will be set to last day of that month. For the date of admission with missing day, the day will be set to first day of that month. If that is before the start of the study phase (within the same month), then the day will be set equal to today of the start of the study phase. Otherwise, if it is before the day of the start of the run-in (within the same month), then it will be set today of the start of

Outliers and influential observations will be identified via graphical plots. Once outliers or influential observations are identified, the study team will be informed and according to their decision the analysis for primary endpoint may be repeated using a statistical method robust against outliers. Additional exploratory analyses will be conducted as deemed appropriate.

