# 7.9.1 Analysis of primary endpoint – study phase - between-treatment difference in TIR (70-180 mg/dL) – non inferiority test

The goal is to assess the non-inferiority in the percentage of time that the sensor glucose measurement is in the target range, 70 to 180 mg/dL (3.9-10.0 mmol/L), during each 12-week period in the Treatment 780G in Auto Mode compared to Control MiniMed 780G in Manual Mode + SBL.

The between-treatment difference will be compared using the following hypotheses:

$$\begin{aligned} H_0: \Delta TIR &\leq -7.5\% \\ H_\alpha: \Delta TIR > -7.5\%. \end{aligned}$$

Where  $\Delta TIR$  is the average of the cross-over differences in time in range in Treatment 780G in Auto Mode vs Control MiniMed 780G System + SBL ( $TIR_{AHCL} - TIR_{SBL}$ ), and the test will be at the 0.025 (one-sided) significance level.

The carryover effect will be tested using repeated measures mixed model with period, randomization sequence, and treatment as fixed effects, and subject as the random effect.

The 97.5% lower confidence limit of between-treatment difference will be calculated. If it is greater than -7.5%, the non-inferiority will be concluded.

If the p value of the coefficient for randomization sequence is ≤0.1 (there is a carryover effect), data from period 1 will be used for analysis only. The 97.5% lower confidence limit of between-treatment difference at period 1 will be calculated. If it is greater than -7.5%, the non-inferiority will be concluded.

Descriptive summary statistics of the primary endpoint will be presented stratified by treatment. In addition, descriptive summary statistics of the primary endpoint will be presented stratified by country.

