#### 7.9.2 Analysis of primary endpoint – continuation phase - betweentreatment difference in HbA1C – non inferiority test

The goal is to assess the non-inferiority in the mean Hba1c during the 12-week continuation phase period 2 in the Treatment MiniMed 780G BLE 2.0 system with the DS5 sensor in Auto Mode compared to Control MiniMed 780G System in Auto Mode. The between-treatment difference will be compared using the following hypotheses:

$$\begin{array}{l} H_0: \Delta HbA1c \geq 0.4\% \\ H_\alpha: \Delta HbA1c < 0.4\%. \end{array}$$

Where  $\Delta HbA1c$  is the difference of the average of HbA1c for Treatment MiniMed 780G BLE 2.0 system with the DS5 sensor in Auto Mode vs Control MiniMed 780G in Auto Mode at the end of the 12-week continuation phase period 2, will be assessed by using of mixed model adjusting by baseline value. It will be tested at the 0.025 (one-sided) significance level.

The 97.5% upper confidence limit of between-treatment difference will be calculated. If it is lower than 0.4%, the non-inferiority will be concluded.

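### If the carryover test triggers, the study-phase primary analysis becomes a period-1 between-child comparison with no baseline covariate specified, although run-in TIR is planned

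*SAP*

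**What the plan says.** SAP 7.9.1 analyses study-phase TIR with a "repeated measures mixed model with period, randomization sequence, and treatment as fixed effects, and subject as the random effect", and "the test will be at the 0.025 (one-sided) significance level". It then sets a switch: "If the p value of the coefficient for randomization sequence is ≤0.1", carryover is declared and "data from period 1 will be used for analysis only. The 97.5% lower confidence limit of between-treatment difference at period 1 will be calculated". That limit is compared with -7.5%. Protocol 14.5.1 has the same rule. Neither document names a model or covariate for the period-1 analysis.

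Baseline data are planned. One purpose of the run-in is "to collect 2 weeks of baseline data" (SAP 5), and protocol 8.5.1 requires at least 70% sensor use over two weeks before randomisation. In the continuation phase the primary endpoint "will be assessed by using of mixed model adjusting by baseline value" (SAP 7.9.2), and the secondary endpoints in SAP 7.9.4 are treated the same way.

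Two data rules bear on the covariate. SAP 7.2 excludes both visit days from the run-in window. SAP 7.4 derives run-in metrics only with "a minimum number of 2880 of SG values (288 SG values/day × 10 days out of 14 days", and otherwise counts them as missing. Protocol 14.4 rules out imputation.

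**The concern.** In the two-period analysis each child is his or her own control. A baseline that is constant within a child cancels there, so leaving it out costs little. Once period 2 is dropped that protection goes, and between-child variance enters the treatment comparison in full. This is where a pre-randomisation measure of the same quantity is most useful.

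The fallback is also not used in a random sample of trials. It is used when the two sequences look different, and without true carryover that means a chance imbalance between the groups of children. The same imbalance sits in the period-1 difference. Run-in TIR measures part of it and can remove that part.

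At stake are the precision and the error rate of the estimate that would decide the study-phase primary endpoint. If the covariate is left open, it would have to be chosen after the switch has occurred, with data in hand.

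**Working it through.** **Inputs from the documents.** About 80 randomised and 72 completing (protocol synopsis), allocated 1:1 (protocol 9.4.1); switch at p ≤0.1; margin 7.5 points; one-sided 0.025. The 10% drop-out in protocol 14.6.1 reproduces the completers: 80 × 0.9 = 72, or 36 per sequence. The text available gives no planning SD, power or correlation, so the sample size itself cannot be re-derived. That is not held against the plan.

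**Assumptions.** SD 8.7 points is the spread reported for real-life 780G users under 15 (SAP 3). It is an illustration, not a planning value for this age group or for Manual Mode. Rho, the run-in to period-1 TIR correlation, is varied from 0.3 to 0.8.

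**Average precision.** Unadjusted SE = SD × √(2/n) = 8.7 × √(2/36) = 2.05 points. Adjusted SE = 2.05 × √(1 − rho²). Variance removed = rho².

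| rho | variance removed | adjusted SE | interval narrower by |
|---|---|---|---|
| 0.3 | 9% | 1.96 | 4.6% |
| 0.5 | 25% | 1.78 | 13% |
| 0.6 | 36% | 1.64 | 20% |
| 0.8 | 64% | 1.23 | 40% |

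At 36 per sequence, simulated reductions were 7%, 36% and 62% for rho 0.3, 0.6 and 0.8. If the arms have different correlations, say 0.7 and 0.3, a common-slope model removes ((0.7 + 0.3)/2)² = 25%.

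**When the fallback is triggered by chance.** The simulation had no carryover, 36 per sequence, SD 8.7, equal correlations among run-in and both periods, and a true difference at the margin of -7.5. The switch occurred in about 10% of trials. Within those trials (independent runs agreed closely; ranges show the spread):

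| rho | RMSE, unadjusted → adjusted | false non-inferiority, unadjusted → adjusted |
|---|---|---|
| 0.3 | 3.65 → 3.28 | 16–17% → 13–14% |
| 0.6 | 3.9–4.0 → 2.5 | 19–21% → 10% |
| 0.8 | 4.1 → 1.6–1.7 | 23–25% → 6–7% |

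The nominal false non-inferiority rate is 2.5%. Adjustment helps at every rho tried, but the conditional rate stays above nominal.

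**Is run-in TIR available?** The 70% criterion over 14 days is 0.70 × 14 × 288 = 2822 readings. The cut-off of 2880 is 2880/4032 = 71.4% of 14 days. The gap is 58 readings, about 5 hours at 5 minutes each. If Visit 3 falls on day 14 and both visit days are excluded, 13 full days remain and 2880 is 2880/3744 = 76.9% of them. A child can therefore qualify for randomisation and still have run-in TIR set to missing.

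**The case against.** **The size depends on rho.** A reader might infer that the fallback discards a third to nearly two-thirds of the available precision. That needs rho of about 0.58 to 0.8, which the documents do not give. Run-in is about two weeks in Manual Mode, while one arm's period 1 is twelve weeks in Auto Mode, so a lower correlation is plausible. At rho 0.3 to 0.5 the loss is 9% to 25%. This objection stands.

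**Baseline for every child.** A reader might also infer that every randomised child has a usable run-in TIR. The 2880-reading rule can blank it, and the ITT set keeps children randomised despite deviations. The 76.9% figure is itself a special case: Visit 3 has a +14-day window, and a longer run-in makes 2880 readings easier to reach. This also stands.

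**Silence is not exclusion.** SAP 7.9.1 names the data and the confidence limit, not a model, so a covariate is not ruled out. That is correct. But the continuation-phase models state their adjustment, and a choice left open here would be made after the switch.

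**Limited impact.** Without carryover the path is taken about one time in ten. At SD 8.7 and a true difference of 0, unadjusted period-1 power is about 95% at 36 per sequence, and the protocol anticipates improved control. This is fair for average power. Conditional on a chance trigger, however, that power is about 67% to 79%. At assumed SDs of 12 and 15 the average power is 75.5% and 56.4%, against 91.2% and 75.5% with adjustment at rho 0.6. Nor does power answer the conditional error in the estimate.

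**HbA1c.** SAP 7.9.3 does not repeat the fallback for HbA1c. Its use there is inferred from the reference back to the primary method in SAP 7.9.3.1 and protocol 14.5.3.

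**Conclusion.** The point holds in a limited form. The period-1 fallback is a between-child comparison that can decide the study-phase primary endpoint, and it has no pre-specified baseline covariate although run-in TIR is planned and the same SAP adjusts for baseline in the continuation phase. The gain from adjustment is about rho squared on the variance scale: modest at 0.3, substantial at 0.6 or above. It also lowers error when the switch occurs by chance. These sizes rest on assumed correlations and, for the simulated errors, on an SD borrowed from an older real-life population. The two-period analysis is not affected. Adjustment would not repair the carryover pre-test itself, which still distorts the conditional error rate.

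**What to change.** In SAP 7.9.1, specify the period-1 analysis as ANCOVA with treatment and run-in TIR. If the fallback is meant to apply to HbA1c, say so in SAP 7.9.3 and use Visit 1 HbA1c as the covariate. That value precedes the run-in and reflects prior therapy, so its correlation is also unknown.

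For this covariate only, derive run-in TIR for any child who met the 70% sensor-use criterion (2822 readings over 14 days). The 2880 cut-off can stay for descriptive run-in metrics.

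State a rule that keeps ITT children with a missing baseline in the analysis, since a complete-case ANCOVA would drop them and protocol 14.4 allows no imputation. One option is to model run-in and period-1 TIR jointly as repeated outcomes with a common run-in mean, which uses available data without imputing.

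The cost is small: one covariate from data already scheduled, and one missing-baseline rule, written before the carryover test is run.

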#### Pass/Fail Criteria:

The study pass/fail criteria are based on statistical hypothesis of the primary endpoint. The study will be considered as success when the evaluation criteria meet the predefined threshold on the ITT set.

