14.1 General Aspects of Analysis

All data collected from the time of screening until the end of the study will be collected on eCRFs and electronically by uploading the various devices. Data and analysis will be summarized in a Clinical Study Report. Any deviations from original statistical plan and the rationale will be described in the Clinical Study Report. Both the study and continuation phases of the study are used for confirmatory analysis.

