14.5 Endpoints and Hypotheses

14.5.1 Analysis of Primary Endpoint – Study Phase

The goal is to assess the non-inferiority in the percentage of time that the sensor glucose measurement is in the target range, 70 to 180 mg/dL (3.9-10.0 mmol/L), during each 12-week period in the Treatment 780G in Auto Mode compared to Control MiniMed 780G System + SBL. The between-treatment difference will be compared using the following hypotheses:

$$\begin{aligned} H_0: \Delta TIR &\leq -7.5\% \\ H_\alpha: \Delta TIR > -7.5\%. \end{aligned}$$

Where ΔTIR is the average of the cross-over differences in time in range in Treatment 780G in Auto Mode vs Control MiniMed 780G System + SBL ($TIR_{AHCL} - TIR_{SBL}$), and the test will be against at the 0.025 (one-sided) significance level.

The non-inferiority absolute margin of 7.5% TIR was chosen in consensus with physicians as the maximum acceptable decrease of TIR in comparison with the current approved therapy. In addition, the non-inferiority margin of 7.5 % TIR is equivalent to a less than 0.3 % change in HbA1c which is considered non clinically significant ³. This is in line with the recommendations from the International Consensus on Time in Range (quoted 'an increase in TIR of 10% (2.4 h per day) corresponded to a decrease in A1C of approximately 0.5% (5.0 mmol/mol)") ³.

D00674412	Version E	Page 75 of 96	Medtronic

Carryover effect will be test using repeated measures mixed model with period, randomization sequence, and treatment as fixed effects, and subject as the random effect.

The 97.5% lower confidence limit of between-treatment difference will be calculated. If it is greater than - 7.5%, the non-inferiority will be concluded.

If the p value of the coefficient of randomization sequence is ≤ 0.1 (there is a carryover effect), data from period 1 will be used for analysis only. The 97.5% lower confidence limit of between-treatment difference at period 1 will be calculated. If it is greater than -7.5%, the non-inferiority will be concluded.

Descriptive summary statistics of the primary endpoint will be presented stratified by study phase, treatment arm, investigational study site and other variables.

Pass/Fail Criteria:

The study pass/fail criteria is based on statistical hypothesis of the primary endpoint. The study will be considered as success when the evaluation criteria meets the predefined threshold for both ITT and PP sets.

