18.7 List of Consumables and Accessories

A list of all compatible consumables and accessories will be kept under a separate cover upon request to the Sponsor.

CIP342 Clinical I				
D00674412	Version E	Page 88 of 96	Medtronic	

19 Version History

Version	Summary of changes	Justification of changes	Potential impact of the change on performance, effectiveness, or safety or other endpoints	Identification of the affected study documents	Author(s)/ Title
A	Not Applicable, New Document	Not Applicable, New Document	Not Applicable, New Document	Not Applicable, New Document	, Sr. Medical
					Writer

CIP342 Clinical Investigation	Plan			
D00674412 Version	E Page 89 c	of 96 Medtronic		
B1) Synopsis and Section 8.3 Inclusion criteria: Inclusion criteria#5 Novorapid [™] added together with Novolog throughout the document	1) Novorapid is the brand name used in Europe for Insulin Aspart	1) None	ICF	, Sr. CRS
2) Synopsis and Section 8.4 Exclusion Criteria: Exclusion criteria #1: added "untreated" to coeliad disease	2) Omitted in previous version by mistake	2) None		
3) Synopsis and Section 8.4 Exclusion criteria: Exclusion criteria #2: comma removed after GLP-1	3) Typographic mistake in the previous version	3) None		
4) Section 5.3 Study Oversight and subsequent section 5.3.1 Steering Committee modified. Removal of the sentence 'and external physicians with an expertise in endocrinology and the management of diabetes including insulin pumps and CGM'	4) No external Steering Committee was finally convene, as DMC and CEC are responsible for study oversight duties.	4) None		
5) Section 6.28 CareLink personal software and Section 6.29 CareLink System software: reference to "Microsoft® Internet Explorer" browser delated	5) Obsolete browser	5) None		
6) Section 9.1 – Visit 1: deleted the word "severe from severe DKA, page 32	 6) Typographic mistake in the previous version 	6) None		
7) Table 6 Pump setting correction f typos	7) Typographic mistake in the previous version	7) None		
8) Section 14.4 Analysis Populations and Handling of Missing Data, Error: PP population definition was changed as following:" The PP population will include all randomized subjects, excluding any subject with at least one of the following deviations	 8) Requested from MHRA to define study deviation for PP exclusion 	8) None		

CIP342 Clinical Inv			
D00674412	Version E	Page 90 of 96	Medtronic

					Potential impa	act of the	Iden	tification	

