#### **Version History** 1.

Version	Summary of Changes	Author(s)/Title
1.0 23 APR 2024	Not Applicable, New Document	/ Sr Statistician
2.0 22 JUL 2024	
 
Par 7.1.3:
 
Updated the Per Protocol population set definition to exclude participants with major protocol deviations, including now non-compliance with randomization assignment
 
Added definition and sensitivity purpose of "As Treated population set" for continuation phase
 
Par 7.10:
 
Specified that safety reporting will be performed by both assigned randomization treatment and actual treatment received
 
	Prin Statistician

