that the MiniMed 780G system helped children over 7 years old to reach better time in range (TIR) and better mealtime glycaemia without increasing time below range (TBR), severe hypoglycemia or ketoacidosis. Furthermore, real-life data analysis in 3,211 users, reporting age <15, demonstrated a GMI of 6.8±0.3%, TIR of 73.9±8.7%, and TBR (70 mg%) of 3.2%, while spending 92.7% of time in AHCL . These studies and real-life usage of the MiniMed 780G system has been shown to improve glycemic control and reduce the burden of management of T1D in children and adolescents. However, studies involving very young children remain limited, and therefore this randomized trial is being conducted to evaluate safe usage of the MiniMed 780G system in comparison with the currently available standard sensor-augmented pump therapy for young children 2 to 6 years old.

This Statistical Analysis Plan (SAP) Version is based on Protocol E 3' OCT 2023, and it has been designed to document, before data is analyzed, the planned statistical analyses for both study and continuation phases and will be used to support the clinical reports. This SAP does not limit the analysis in reports, and additional analyses of the study data beyond this plan might be conducted. However, this document provides the basis for the statistical sections of the clinical reports. Analyses not planned in the SAP and incorporated into the final report will be referred to as "not prespecified". Moreover, in case any analyses will be done differently than planned in the CIP or SAP, an explanation will be provided in the final reports.

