# CIP342 LENNY Statistical Analysis Plan Form Revision 2.0 Page 14 of 31 Medtronic • Per Protocol (PP) Population:

For both, study phase and continuation phase, the PP population will include all randomized subjects in the respective phase, and excluding any subject with at least one of the following deviations (to be assessed independently in each phase):

- Auto Mode use during is less than 75%
- Sensor use is less than 70%
- o Subject did not complete the specific phase, respectively
- Subject did not meet screening criteria for the specific phase but continued the phase
- Subject did not meet randomization criteria for the specific phase but continued the phase
- o Subject not compliant with the assigned randomization treatment

For sensitivity purposes, efficacy analysis of the primary and secondary endpoints will also be performed in the Per Protocol set.

The criteria listed above will be assessed separately for study and continuation phase, respectively, and separate ITT and PP population sets will be defined accordingly.

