#### 7.11 Changes to Planned Analysis

The analysis described in the CIP could differ from that presented in this SAP due to data availability. Any deviation from the original statistical plan will be described and justified in the final report, as appropriate.

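### The study-phase TIR endpoint has two success rules (ITT and PP in the protocol, ITT only in the SAP), and the protocol's HbA1c decision sentence is reversed

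*SAP*

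**What the plan says.** **TIR, study phase.** Protocol 14.5.1 and SAP 7.9.1 set the same test: the 97.5% lower confidence limit for Auto Mode minus Manual Mode must lie above -7.5 percentage points. They differ on where it must be met. Protocol 14.5.1: "The study will be considered as success when the evaluation criteria meets the predefined threshold for both ITT and PP sets". SAP 7.9.1: "The study will be considered as success when the evaluation criteria meet the predefined threshold on the ITT set".

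The SAP is consistent with itself. Section 7.1.3 states "For sensitivity purposes, efficacy analysis of the primary and secondary endpoints will also be performed in the Per Protocol set", and section 7.4 likewise treats PP as sensitivity. Section 3 states "This Statistical Analysis Plan (SAP) Version is based on Protocol E", which is the version that carries the joint rule.

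On departures, SAP 7.11 says "The analysis described in the CIP could differ from that presented in this SAP due to data availability" and then promises that deviations will be described and justified in the final report. SAP 3 and protocol 14.1 make similar promises.

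**HbA1c, continuation phase.** Protocol 14.5.2 and SAP 7.9.2 share the same hypotheses: the null is a difference (new system minus current system) of 0.4% or more, the alternative a smaller one. The protocol then concludes non-inferiority if the 97.5% lower limit is above 0.4%. The SAP does so if the 97.5% upper limit is below 0.4%.

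**The concern.** The protocol states that "Both the study and continuation phases of the study are used for confirmatory analysis". A confirmatory endpoint needs one success rule, settled before anyone sees the result. Here two are in force, and the supplied text has no clause saying which document governs. If ITT passes and PP does not, the sponsor could report success by citing the SAP and a reader could report failure by citing the protocol. Nor does the SAP say that its rule differs from the protocol's.

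The HbA1c sentence is a smaller matter. Read literally, it would declare non-inferiority only for a system shown to be more than 0.4% worse.

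**Working it through.** **Step 1. The two TIR rules side by side**

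| ITT | PP | Protocol 14.5.1 | SAP 7.9.1 |
|---|---|---|---|
| pass | pass | success | success |
| pass | fail | failure | success |
| fail | pass | failure | failure |
| fail | fail | failure | failure |

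The conflict is confined to the second row. It follows from the text and needs no assumption.

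**Step 2. Type I error.** A 97.5% one-sided limit gives 1 - 0.975 = 0.025, as both documents state. Requiring a second set to pass can only lower this. At a true difference of -7.5 (assumed SD 12, ITT 72), simulation gives 0.025 for ITT only and about 0.018 to 0.010 for both sets, with PP sizes from 65 down to 43.

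**Step 3. How often the second row occurs.**
- From the documents: margin 7.5 points; about 80 randomised and 72 completing the study phase (protocol synopsis). The stated 10% dropout reproduces this: 80 x 0.9 = 72.
- Assumed, because the supplied text does not give them: SD of the within-child TIR difference 8, 10 or 12 points; ITT contributing 72 or 80 children; PP 50, 58 or 65 of them.
- Pass in a set of size n: mean - t(0.975, n-1) x SD/sqrt(n) > -7.5.
- 100,000 simulated trials per scenario, with PP nested in ITT. The mixed model and the carryover step are left out.

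Probability of ITT pass with PP fail, range over all SDs and set sizes:

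| True difference | Equal effects | PP children 5 points better | PP children 5 points worse |
|---|---|---|---|
| +5 | 0% | – | below 0.01% |
| 0 | under 1% | at most 0.05% | 0-10% |
| -2.5 | 0.1-14% | up to about 1% | 0.5-51% |
| -4 | 3-23% | up to about 2% | 10-68% |

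**Step 4. A single example.** Take SD 10, ITT 80, PP 58.
- ITT half-width: 1.990 x 10/sqrt(80) = 2.225.
- PP half-width: 2.002 x 10/sqrt(58) = 2.629.
- An observed difference of -4.9 in both sets gives lower limits of -4.9 - 2.225 = -7.13 (pass) and -4.9 - 2.629 = -7.53 (fail).
- With equal observed means, the rules disagree between -7.5 + 2.225 = -5.27 and -7.5 + 2.629 = -4.87.

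**Step 5. HbA1c.** Let L and U be the lower and upper limits. If L > 0.4 then U > L > 0.4, so the protocol sentence and the SAP rule cannot both hold for any data. An interval of -0.30 to 0.30 is non-inferior under SAP 7.9.2 and not under the protocol sentence. For scale, assume 32 per arm (64 completers at 1:1) and SD 0.6 to 1.0, so SE = SD x sqrt(2/32) = 0.15 to 0.25. With a true difference of 0, the SAP rule concludes non-inferiority with probability Phi(0.4/SE - 1.96) = 0.76 to 0.36; the protocol sentence does so with probability 1 - Phi(0.4/SE + 1.96) = 0.000002 to 0.0002.

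**The case against.** **The rules will seldom disagree.** This stands. Both documents' background sections lead one to expect Auto Mode to improve TIR, and at +5 the rules agree in essentially every trial. Material disagreement needs Auto Mode to be truly some points worse, or PP children to do clearly worse than the others. The largest figures need both, and the SDs, PP sizes and effect differences are all assumed. The omitted carryover step does not help the objection, though. If the sequence test sends the analysis to period 1 only (about 10% of trials with no true carryover), a parallel comparison with an assumed 40 per arm, PP 25-32 per arm and between-child SD 8-12 gives disagreement in 3-23% of those trials at a true difference of 0, and up to 4.6% at +5.

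**ITT only may be the better rule.** PP selects children on device use after randomisation, and protocol 14.4 already puts the primary and secondary efficacy analyses on an ITT basis. This also stands, which is why either rule is acceptable. It does not excuse having two.

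**Departures will be explained in the final report.** That commitment is real and covers disclosure. It comes after the results, so it cannot settle a success rule in advance.

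**Stronger readings that a reader might infer:**
- *The SAP relaxed the rule without logging it.* Its version history includes "Updated the Per Protocol population set definition to exclude participants with major protocol deviations, including now non-compliance with randomization assignment" and does not mention pass/fail. But it lists only changes from SAP 1.0 to 2.0, and 1.0 is a new document, so its silence does not show when or why the ITT-only rule came in.
- *A regulator required PP to pass.* The protocol's version history records "Requested from MHRA to define study deviation for PP exclusion". That is a request to define the exclusions; nothing in it makes PP a success condition.
- *The secondary tests must wait for both sets.* Protocol 14.5.3 opens the sequence when the primary analysis is significant and tests secondaries on ITT. A two-set gate is not written there.

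**Conclusion.** The concern holds as a conflict between two written success rules for the study-phase TIR primary endpoint. That rests on the text alone. The size rests on the assumptions listed: with equal effects in PP and non-PP children, disagreement is nil at +5, under 1% at 0 and roughly 3-23% at -4. It would be wrong to conclude that the type I error is inflated or that the study's verdict is likely to change if Auto Mode works as expected. It still needs settling before analysis, because a choice between the two rules made after the result is known would not be credible.

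The HbA1c sentence in protocol 14.5.2 is a drafting error. The protocol's own hypotheses point the right way and the SAP states the rule correctly, so an analysis run from the SAP would not be affected.

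**What to change.** Before analysis, put one TIR success rule in both documents. Either option is acceptable.

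- **(a) Joint rule.** Change SAP 7.9.1 so that the lower limit must exceed -7.5% in both the ITT and PP sets, matching Protocol E. PP then decides the verdict, so protocol 14.4 and SAP 7.1.3 need one PP definition. At present only the SAP excludes children who did not comply with their assigned treatment. Auto Mode use should be measured over the assigned Auto Mode period: averaged over both 12-week periods, a fully compliant child reaches only about 12/24 = 50%, below the 75% cut-off.
- **(b) ITT only.** Amend protocol 14.5.1 to ITT with a stated justification, and keep PP as sensitivity.

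The gate to the secondary tests follows whichever rule is chosen; say so in protocol 14.5.3 and SAP 7.5.1.

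Separately, correct protocol 14.5.2 to conclude non-inferiority when the 97.5% upper limit is below 0.4%, as in SAP 7.9.2.

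**Cost.** Wording changes and a protocol amendment (14.5.2 in any case; 14.4 and 14.5.3 as well under (a); 14.5.1 and 14.5.3 under (b)), with the ethics committee and authority approvals in protocol 15.1. No new data. Under (a), success is harder to reach than under the SAP's rule: by under 1 percentage point at a true difference of 0 and up to about 23 points at -4, with equal effects.
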